9.3. Sample Size

The sample size of 32 subjects completing this study was based on the estimated primary efficacy variable response rates for the most effective active medication and vehicle, which are expected to be approximately 60% and 10% respectively. This difference is expected to yield approximately 88% power using a standard chi-square test under the assumption of lesion independence.

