1. SYNOPSIS

Title:

A Randomized, Double-Blind, Vehicle-Controlled, Within Subject Comparison Study of the Safety, Tolerability and Effectiveness of A-101 Topical Solution in Subjects with Seborrheic Keratosis.

Objectives:

The main objective of this study is to evaluate the safety and effectiveness of A-101 (hydrogen peroxide) Solution 25%, 32.5% and 40% when applied to individual seborrheic keratosis (SK) target lesions on the back compared with a matching A-101 Solution Vehicle.

Methodology/Study Design:

The duration of study participation is anticipated to be a maximum of 95 days per subject. This includes the up to 14-day screening period, a visit for a required study medication application, a 21-day no treatment period, a visit for an optional study medication retreatment application, a 56-day no treatment follow-up period and a maximum allowable 4-day Visit 9 visit window. Study visits are:

- Visit 1 (Day -13 to 0) enrollment; start screening period
- Visit 2 (Day 1) randomization; study medication application
- Visit 3 (Day 8) no treatment follow-up
- Visit 4 (Day 15) no treatment follow-up
- Visit 5 (Day 22) follow-up visit where target lesions that meets the retreatment criteria will receive a second study medication application
- Visit 6 (Day 29) no treatment follow-up
- Visit 7 (Day 43) no treatment follow-up
- Visit 8 (Day 57) no treatment follow-up
- Visit 9 (Day 78) no treatment follow-up; end of study.

During Visit 1 the investigator will, for each subject, identify 4 individual SK lesions (target lesions) on the back for treatment, perform an electrocardiogram (ECG) and collect blood samples for clinical laboratory safety tests to determine the subject's eligibility for randomization. Subjects may have more than 4 SK lesions on the back, or on other body surfaces, but only the target lesions on the back will be evaluated and treated.

During Visit 2, eligible subject's target lesions will be randomized, each to receive 1 study medication (a unique study medication for each target lesion) and then the study medication applications will be performed. Every eligible subject will receive all 4 of the study medications.

At Visits 3 and 4, subjects will be seen for a no treatment follow-up.

At Visit 5, subjects will be seen for follow-up and any target lesion that meets the re-treatment criteria (*i.e.*, Physician's Lesion Assessment [PLA] >0) will receive a second study medication application.

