At Visits 6-8, subjects will be seen for a no treatment follow-up.

At Visit 9, subjects will be seen for a no treatment follow-up and discharged from the study.

Number of Subjects:

Approximately 36 subjects will be enrolled in this study at one United States investigational center with the goal to have 32 subjects complete the study.

Diagnosis and Main Criteria for Inclusion:

Subjects will be adult males and females with 4 clinically typical appearing seborrheic keratosis target lesions on the back.

Study Medications, Application, and Mode of Administration:

There are 4 study medications for topical application:

- A-101 Solution 25%
- A-101 Solution 32.5%
- A-101 Solution 40%
- A-101 Solution Vehicle.

Study medications will be randomly assigned to the 4 target lesions on each subject's back; each subject will have all the 4 study medications applied, 1 study medication to each individual target lesion.

There are 16 treatment groups. Each treatment group consists of one of 8 randomly-selected permutations for applying each study medication to one of the four target lesions per subject.

At Visit 2, eligible subjects will be randomized to one of the treatment groups (determining the study medication that will be applied to each individual target lesion) in a blinded manner. After randomization an investigational center staff member other than the investigator, will perform, the study medication applications.

At Visit 5, any lesion that meets the retreatment criteria (*i.e.*, PLA >0) will receive a second study medication application.

Duration of Treatment:

The planned treatment and study duration are:

- Enrollment period: approximately 35 days
- Subject participation period: up to 95 days
- Study duration (first subject first visit through last subject last visit): approximately 130 days.

Evaluations - Effectiveness:

The investigator will evaluate the average overall severity of each SK target lesion using the Physician's Lesion Assessment (PLA) and the subject will evaluate each target lesion using the Subject's Self-Assessment (SSA). The investigator will measure Lesion Dimensions (*i.e.*, surface area and thickness) throughout the study for each target lesion.

Evaluations - Safety:

Local Skin Reactions (LSR) for each target lesion, clinical laboratory safety tests, ECGs, vital sign readings, concomitant therapies, urine pregnancy tests and adverse events (AEs) will be monitored throughout the study.

Evaluations - Other:

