9. STATISTICAL ANALYSES

9.1. Statistical Analysis of Clinical Indices

The primary effectiveness analyses will be pairwise comparisons between Vehicle and each active study medication, based on mean change from Visit 2 PLA, using a repeated-measures Analysis of Covariance model suitable for the study design. Study medication concentration is the within-subject independent variable. The Visit 2 score will be the covariate. The primary analysis visit will be Visit 9. An exploratory dose-response analysis may be conducted across concentrations to evaluate a concentration trend, as well as an exploratory longitudinal analysis across visits to evaluate trends over time.

Secondary efficacy analyses will include a similar analysis of SSA, SSK and other evaluations suitable for analysis as continuous variables. Separate primary and secondary effectiveness analyses at each post-baseline visit will be conducted. In addition, secondary analyses will be performed on proportion of PLA and SSA responders, where a subject will be considered a responder if the Visit 9 score is 0. A similar analysis will be done at Visit 5. Chi-square will be used to analyze differences in response rates under the assumption that lesions within a subject may be treated independently, along with a repeated-measures logistic regression model applied as an optional exploratory analysis method.

For all analyses two-tail alpha will be set at 0.05 with no adjustment for multiplicity due to the exploratory nature of the study. The Intent-to-Treat (ITT) population, defined as subjects with data for both Visit 2 and at least one post-Visit 2, will be the primary analysis population, supplanted by analyses of the Per-Protocol (PP) population defined as ITT subjects with no missing effectiveness data and no major protocol violations. ITT population analyses will use last-observation-carried-forward to impute missing post-Visit 2 data.

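### Section 9.3's 88% power is the figure for 16 lesions per arm; the design gives 32 per arm and 99.6% power, and the test that was powered is not the primary analysis

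*Combined protocol and SAP*

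**What the plan says.** All the inputs are in the combined protocol and SAP.

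- **Sample size and rates (Section 9.3).** "The sample size of 32 subjects completing this study was based on the estimated primary efficacy variable response rates" for the best active medication and vehicle, "which are expected to be approximately 60% and 10% respectively". The power statement follows: "This difference is expected to yield approximately 88% power using a standard chi-square test under the assumption of lesion independence".
- **Alpha (Section 9.1).** "For all analyses two-tail alpha will be set at 0.05 with no adjustment for multiplicity due to the exploratory nature of the study".
- **Design (Section 1, Synopsis).** "Every eligible subject will receive all 4 of the study medications", and "each subject will have all the 4 study medications applied, 1 study medication to each individual target lesion".
- **Primary analysis (Section 9.1).** Each active medication is compared with vehicle "based on mean change from Visit 2 PLA, using a repeated-measures Analysis of Covariance model suitable for the study design", with Visit 9 as the primary visit. The proportion of responders (a score of 0) and its chi-square test are listed as secondary.

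**The concern.** The design is within-subject, so the number of lesions on each medication equals the number of completing subjects. A difference of 50 percentage points with 32 observations per arm should have power close to 100%, so 88% looks too low.

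The calculation also concerns a different analysis from the primary one. Section 9.3 says that the size was "based on the estimated primary efficacy variable response rates for the most effective active medication and vehicle", but Section 9.1 treats the responder rate as secondary and tests the primary variable as a mean change.

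This paragraph is the only justification of the sample size. As written, it puts the chance of missing a 60% versus 10% difference at about 12%, when under the plan's own assumptions it is about 0.4%. A reader would overestimate the smallest difference that the study can detect, and that affects how a negative result at 25% or 32.5% is interpreted. The wording also leaves room to argue later about which result was primary.

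**Working it through.** **Inputs.** p1 = 0.60, p2 = 0.10 and 32 completers (Section 9.3); two-sided alpha 0.05 without adjustment, so z = 1.96 (Section 9.1); one lesion per medication per subject (Section 1), so n = 32 lesions per arm. Lesions are treated as independent, as Section 9.3 assumes.

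**Formula** (two proportions, pooled variance under the null):

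power = Φ{ [ (p1 − p2) − 1.96·√(2·p̄(1 − p̄)/n) ] / √( [p1(1 − p1) + p2(1 − p2)]/n ) }

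with p̄ = (0.60 + 0.10)/2 = 0.35, 2·p̄(1 − p̄) = 2 × 0.35 × 0.65 = 0.455, and p1(1 − p1) + p2(1 − p2) = 0.24 + 0.09 = 0.33.

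**Step 1. Reproducing the plan's figure.** With n = 16 per arm:

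- √(0.455/16) = 0.1686 and √(0.33/16) = 0.1436
- (0.5 − 1.96 × 0.1686)/0.1436 = 1.18, so power = **88.1%**

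The neighbouring values are 85.8% at n = 15 and 90.1% at n = 17. Solving for 88% power returns 16 per arm.

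**Step 2. The design as written.** With n = 32 per arm:

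- √(0.455/32) = 0.1192 and √(0.33/32) = 0.1016
- (0.5 − 1.96 × 0.1192)/0.1016 = 2.62, so power = **99.6%**

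**Step 3. Does another formula give 88% at 32 per arm?**

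| Method, n = 32 per arm, 60% vs 10% | Power |
|---|---|
| Pooled formula | 99.6% |
| Exact enumeration, chi-square | 99.6% |
| Exact enumeration, Yates correction | 98.9% |
| Exact enumeration, Fisher | 99.1% |
| Arcsine | 99.5% |
| Noncentral chi-square, 1 df | 98.7% |
| Noncentral chi-square, 3 df | 95.5% |
| Pooled formula, alpha 0.05/3 | 98.3% |
| Pooled formula, alpha 0.01 | 97.1% |
| McNemar (normal approximation), within-subject correlation −0.2 | 97.9% |
| McNemar, correlation 0 | 99.0% |
| McNemar, highest positive correlation these rates allow | 99.8% |

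The lowest value is 95.5%. Neither the choice of formula, nor rounding, nor a stricter alpha of 0.05/3 or 0.01 explains 88%.

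**Step 4. What 88% means with 32 per arm.** Keeping vehicle at 10%, the pooled formula gives 80.6% power for an active rate of 40%, 88.4% for 44% and 89.9% for 45%. So 88% power corresponds to about 44% versus 10%.

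**Step 5. The primary analysis.** The documents give no SD, mean difference or within-subject correlation for PLA change, so its power cannot be computed. A standardised approximation is possible: treat each active-versus-vehicle contrast as a paired t-test on 32 within-subject differences (31 df, critical value 2.04). For a mean difference of 0.57 SD of the paired difference, the noncentrality is 0.57 × √32 = 3.22 and the power is 87.8%; at 0.58 SD it is 88.8%.

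**The case against.** Five points can be made for the plan.

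- **The origin of 16 per arm is not documented.** This stands. The numerical match suggests 16 per arm but does not show why. The figure may have been carried over from another design: Section 9.2 tabulates safety data by an abrasion cohort that is defined nowhere, and the Synopsis mentions 16 treatment groups but 8 permutations. Two cohorts of 16 would fit. That would explain the figure but would not make it right for this trial.
- **The match depends on the formula.** This also stands. At 16 per arm, exact enumeration of the chi-square test gives 90.1% and Fisher 78.6%. The finding does not rest on the match, because no method in the table gives 88% at 32 per arm.
- **The wording on the primary variable can be read more kindly.** It may mean response rates on the PLA scale, PLA being the primary variable. Even so, the powered test is the secondary chi-square and not the ANCOVA on mean change, and the wording blurs this.
- **The 0.57 SD figure is not the power of the planned ANCOVA.** Correct. It is a paired t-test approximation that ignores the baseline covariate, and it should be labelled so.
- **The consequences are limited.** The error is on the safe side, the study is described as exploratory, and Section 9.3 promises power only for the most effective medication. A negative result at another concentration would be judged mainly from its estimate and confidence interval. This limits the harm, but it does not justify keeping a power figure that contradicts its own inputs.

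**Conclusion.** The concern holds. Under the plan's own assumptions (32 completers, one lesion per medication each, 60% versus 10%, independent lesions, two-sided 0.05), power is 99.6% and not 88%. The risk of missing that difference is about 0.4% instead of 12%, roughly 27 times smaller than stated (12/0.44). Allowing for within-subject pairing leaves the power between 97.9% and 99.8% over the correlations examined.

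The figure also belongs to a secondary analysis, and the plan states no power or detectable difference for its primary one. The comparison described is not underpowered; the defect is that the stated justification does not support the number it is meant to justify.

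**What to change.** Rewrite Section 9.3 to do the following:

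1. State that 32 completers, each with one lesion per medication, give over 99% power for 60% versus 10% on the responder endpoint, or about 88% power for 44% versus 10%, by chi-square at two-sided 0.05 with lesions taken as independent.
2. Describe the responder rate as a secondary endpoint, in line with Section 9.1.
3. Add a detectable difference for the primary contrast in PLA change: for example, 0.57 SD of the within-subject difference at about 88% power, labelled as a paired t-test approximation to the ANCOVA. If the sponsor has an SD, express it in PLA grades as well.

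When editing, check whether the 88% was carried over from another design, and reconcile the paragraph with the abrasion cohort in Section 9.2 and the count of treatment groups and permutations in the Synopsis.

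The cost is the rewording of one paragraph, plus that consistency check. No subjects, visits or procedures are added, and the enrolment target stays the same.

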10. TRAINING, MONITORING, DATA MANAGEMENT AND QUALITY ASSURANCE

10.1. Training

For each investigational center there will be an initiation visit prior to enrolling any study subjects.

It is strongly recommended that all investigators, other evaluators, study nurses, study coordinators or other applicable personnel attend this visit. During this visit, participants will be trained to the protocol, study specific procedures, and the CRFs. Those unable to attend the initiation visit must receive on-site training prior to participating in any of the procedures and evaluations in this study.

Clinical Research Associates (CRAs) and other applicable personnel will be trained prior to study initiation to familiarize CRAs with the disease, the Standard Operating Procedures (SOPs), the protocol and other study specific items. Team organization, communication and operational issues will also be discussed.

Aclaris Therapeutics, Inc. will provide an investigational center file to each center.

10.2. Monitoring

The conduct of the study will be closely monitored by representatives of Aclaris Therapeutics, Inc. to verify adherence to ICH Good Clinical Practice (GCP) guidelines and applicable SOPs. Reports of these verifications will be archived with the study report. The investigator will allow the Aclaris Therapeutics, Inc. representatives designee and/or any regulatory agency to have direct access to all study records, CRFs, corresponding subject medical records, study medication dispensing records and study medication storage area, and any other documents considered source documentation. The investigator also agrees to assist the representative, if required.

10.3. Data Management

Data-management activities of this study will be sub-contracted.

Edit checks and review processes will be performed by the sub-contractor until all data clarifications are resolved. The data will be exported to be stored in SAS datasets (or equivalent) by the sub-contractor. After all data clarifications are resolved and subject's evaluability is determined, the database will be locked.

10.4. Quality Assurance

The study is conducted under the sponsorship of Aclaris Therapeutics, Inc. in compliance with the applicable regulatory requirements as well as applicable ICH guidelines, Helsinki Declaration, and in respect of the Aclaris Therapeutics, Inc. and/or sub-contractor SOPs for study conduct and monitoring.

Audits may be carried out by the Aclaris Therapeutics, Inc. or Aclaris Therapeutics, Inc.'s representatives and inspections may be performed by regulatory authorities or IRB/ECs before, during or after the study. The investigator will provide the auditing/inspecting group direct access to all study records (*e.g.*, CRFs, subject medical records, study medication dispensing records) and the investigational center study facilities. The investigator and study staff will be available and will assist the auditing/inspecting groups as appropriate.

11. ETHICS AND GENERAL STUDY CONDUCT CONSIDERATIONS

11.1. Institutional Review Board (IRB)/Ethics Committee (EC)

This protocol, informed consent form, any information provided to subjects, subject recruiting advertisements, and any amendments to these items will receive IRB/EC approval prior to use.

The IRB/EC must receive a copy of the Investigator's Brochure, all protocol amendments, safety reports and other study related information as required by regulation or the IRB/EC procedures.

11.2. Ethical Conduct of the Study

The rights, safety and well-being of the subjects are the most important considerations in this study and take priority over the interests of society and science.

This study will be conducted in accordance with the ethical principles originating from the Declaration of Helsinki, the ICH E6 GCP guideline, local regulatory requirements and, at US investigational centers, in compliance with the HIPAA. The study will be conducted in compliance with the IRB/EC approved version of the protocol and any applicable amendments.

This protocol, informed consent form, any information provided to subjects, subject recruiting advertisements, and any amendments to these items will receive IRB/EC approval prior to use. Subjects will provide voluntary informed consent prior to initiation of any study related procedures.

11.3. Subject Information and Consent

All subjects who participate in this study must be fully informed about the study in accordance with the GCPs, federal regulations, local regulations and, at US investigational centers, with HIPAA. The ICF will contain all the required elements in compliance with the current ICH E6 GCP guideline, local regulatory requirements and, at US investigational centers, in compliance with HIPAA.

The investigator must have a defined process for obtaining voluntary informed consent from every subject.

The ICF, approved by an IRB/EC, will be fully explained to the subject. Prior to any study related procedures, including washout from therapies, the subject will voluntarily sign and date the ICF. The investigator must maintain each subject's ICF in the investigational center's study file and must provide each subject with a copy of the signed and dated ICF.

11.4. Study Conduct and Protocol Amendments

With the exception of eliminating an immediate hazard to a subject, the investigator should not deviate from the protocol or implement any changes without prior written approval from the Aclaris Therapeutics, Inc. and prior review and documented approval from the IRB/EC.

Changes that involve only logistical or administrative changes are allowed. The investigator should document and explain any deviation from the protocol.

11.5. Regulatory Documents

The investigator must maintain a study file containing current and complete regulatory documentation in compliance with the current ICH E6 GCP guideline. This file will be reviewed as part of the routine monitoring for this study.

11.6. Contractual Requirements

A contractual agreement will be signed between Aclaris Therapeutics, Inc. and each investigator. This document will contain supplemental information, including financial terms, confidentiality, study schedule, third party responsibility, and publication rights.

11.7. Data Collection and Archiving

11.7.1. Data collection

The Investigator must maintain required records for all study subjects. Data for this study will be recorded in the subject's source document and on the CRFs. All data on these CRFs should be recorded completely and promptly. A copy of the completed CRFs for each subject will be retained by the investigational center.

11.7.2. Source documentation

Investigators must keep accurate separate records (other than the CRFs) of all subjects' visits that include all pertinent study related information. A statement should be made indicating that the subjects have been enrolled in this clinical study, and have provided written informed consent. Any AEs must be completely documented.

Source documentation includes results of any diagnostic tests conducted during the study.

11.7.3. Archiving

All pertinent data, samples, photographs, correspondence, original or amended protocol, reports and all other material relating to the study will be maintained securely in Aclaris Therapeutics, Inc. /contract research organization/investigator archives for the legally required duration for archiving.

The investigator should maintain the essential study documents as specified in ICH GCP, and in compliance with all regulatory requirements. The investigator should ensure these documents are protected from accidental destruction or disposal.

If the Investigator needs to re-assign responsibility for maintaining these documents (*e.g.*, due to retirement) it must be transferred to a person willing to accept this responsibility. The investigator must notify the Aclaris Therapeutics, Inc., in writing, of the name and address of the new individual.

